**15.0 Statistical Considerations**

Patients will be randomized with a 1:1 allocation ratio into either the microfracture plus losartan versus microfracture alone group. Block randomization will be used with block sized of n=8 to ensure that groups are of approximately equal size at study completion, even if some patients are lost to follow-up or unenrolled.

Intent-to-treat analysis will be performed. We will compare group means, with the hypothesis that greater post-operative PROs and higher graft quality as assessed with quantitative imaging will be observed in the microfracture plus losartan group compared to microfracture alone. Analysis of Covariance (ANCOVA) or Linear mixed-effect models with random intercepts will be used to compare groups while adjusting for the baseline measurement of each subject.

The effect size of microfracture plus losartan compared to microfracture alone with respect to patient reported outcomes is unknown, so a sample size calculation was performed based on anticipated quantitative

Anticipated effect sizes for the group difference with respect to MRI-assessed cartilage quality were derived from the literature, however a paucity of helpful literature was found in the hip literature. Sample size for this study was determined via a statistical power analysis using published data from Apprich, et al , who compared patients treated with microfracture of the talus versus patients treated with matrix-associated autologous chondrocyte transplantation (MACT).

The primary outcome metric reported in Apprich, et al was a semi-quantitative scale of diffusion-weighted imaging (DWI) acquired by MRI and the paired differences between DWI of the repaired tissue and healthy reference cartilage for each patient was reported for each treatment group. We aim to power this study to detect an effect size between the microfracture alone and microfracture plus losartan groups that is equal to the observed between-group effect size calculated from Apprich, et al (d=1.107).

The significance level will be set at  $\alpha=0.05$ . Assuming 2-tailed testing and requiring 90% statistical power, 19 patients per group are sufficient to detect the effect size of interest. We aim to enroll 20 subjects per group. Power calculations were performed using G\*Power (version 3.1; Universität Düsseldorf).

---

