| Screening Tools:
(At preoperative visit) | 
Standard of Care Data Collected
 
Basic demographic data, medical and surgical history, medication review, age, gender, body mass index and chronicity of the injury, co-morbidities, smoking status, range of motion, strength and size of the cartilage lesion will be recorded. Circumduction evaluation exercises and range of motion restrictions will be evaluated. Patient Reported Outcomes (PRO) tools which will be repeated, at key study intervals will be performed and a T2 MRI of the hip will be performed as standard of care diagnosis.
  |
| Subject Follow-up:                          | 
All adverse events will be assessed during Study Medication administration and for 5 days (+/- 3) days after medication completion. After Study Medication administration only those adverse events related to the target hip will be collected. In addition, the following data will be collected:
 
Visit 1: Post Op Day 1:
 
Subject discharge for the hospital is anticipated to occur on POD1. At discharge the subject will be provided with a blood pressure cuff and be trained on “at home” blood pressure monitoring and recording. They will also be provided with a prescription for Study Medication which will be written in a blinded format for either losartan or placebo. Subjects will be instructed to visit the Vail Hospital Pharmacy to obtain the correct, blinded Study Medication. Study Medication Logs, and Blood Pressure Logs will be provided, with instructions for completion.
 
Subjects will be instructed to undergo post-operative physical therapy, and they will be provided with a document outlining recommended content. They will also be provided with a
 |

|  |   |
|--|---|

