### **10.3 Enrollment Criteria**

#### **10.3.1 Inclusion Criteria**

Patients who:

1. Are aged 18-60 at time of surgery;
2. Tonnis grade 1 or less;
3. Present with a single, localized, grade 3 or 4 cartilage lesion of the acetabulum or femoral head treated with primary BMS (microfracture) performed by [name].

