## **11.0      Study Procedures**

Patients who present for treatment and in whom operative treatment has been planned, will as part of their pre-operative evaluation undergo a standard of care medical review. Basic demographic data will be collected, including age, gender, body mass index, chronicity of the injury, and surgical data will be queried. Additional data including medical co-morbidities, smoking status, medication use, will be collected. History of hip trauma, range of motion, strength, size of the cartilage lesion, circumduction evaluation exercises and range of motion restrictions will be evaluated. As standard of care, patients complete several Patient Reported Outcomes (PRO) tools which will be repeated, at key study intervals as described in the following section of this document, should the patient consent to participate in the study. Subjects will also undergo a T2 MRI of the hip as standard of care diagnosis.

These routine baseline measurements will be used to evaluate preliminary eligibility. If eligibility seems likely, a member of the Study Team will briefly describe this study and gauge the patient's interest in participation.

A full Study Schemata is provided in [Appendix B](#).

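### Adding preoperative lesion size to the baseline-adjusted models is a cheap possible gain in precision; the plan as written is not in error

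*Combined protocol and SAP*

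**What the plan says.** - **Model and covariates.** Section 15.0 leaves the model open between ANCOVA and a random-intercept mixed model. Whichever is chosen is to "compare groups while adjusting for the baseline measurement of each subject". The Statistical Methods row of the synopsis (section 3.0) says the same. Neither names a further covariate.
- **Randomisation.** Section 15.0 specifies 1:1 allocation in blocks of 8. No stratification factor is given.
- **Lesion size.** The synopsis lists it among the preoperative data: "range of motion, strength and size of the cartilage lesion will be recorded". Section 11.0 agrees: "strength, size of the cartilage lesion, circumduction evaluation exercises and range of motion restrictions will be evaluated". The schedule in Appendix B has no row for it.
- **Lesion site.** Section 10.3.1 admits patients with a "single, localized, grade 3 or 4 cartilage lesion of the acetabulum or femoral head". Site is not listed anywhere as a recorded data item. The nearest statement is in section 11.0, that "surgical data will be queried".

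**The concern.** The trial is small and pools lesions of different sizes at two sites. The primary MRI outcome describes repair tissue formed after surgery, whereas the baseline T2 scan is taken before surgery and cannot measure that tissue. The baseline value may therefore miss prognostic information that lesion size carries, although the documents give no correlation to settle this.

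Any prognostic variation left out of the model stays in the error term and widens the interval for the treatment effect. This matters more if the true effect is below the design value. That value, d=1.107, comes from a study of a different joint (talus), a different comparison (chondrocyte transplantation against microfracture) and a different measure (diffusion-weighted imaging). Covariates added after unblinding would be open to challenge, so the choice has to be made beforehand.

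**Working it through.** **Inputs from section 15.0.** Two-sided alpha 0.05, power 90%, d=1.107, 19 per group required, 20 per group to be enrolled.

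**Assumptions, not in the documents.** R2 for lesion size of 0, 0.10, 0.20 or 0.30, and a smaller effect of d=0.8 alongside the design value. Effects are expressed in residual SDs after baseline adjustment.

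**1. The plan's own figure.** The exact two-sample t-test at d=1.107 gives power of 89.7% with 18 per group, 91.3% with 19 and 92.7% with 20. The stated 19 per group is reproduced, and it does not depend on the covariate question.

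**2. How likely chance imbalance is.** With 20 per arm, the difference in mean lesion size has a standard error of √(2/20) = 0.316 SD. The probability that it exceeds 0.3 SD in either direction is P(|Z| > 0.3/0.316 = 0.949), about 34%.

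**3. Power with covariates.** For k covariates and N=40:

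- error df = N − 2 − k
- variance factor v = (1 − R2) × [1 + k/(N − k − 3)], where the bracket is the expected cost of chance covariate imbalance between arms
- noncentrality = d / √(v × 2/20)

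Baseline value only (k=1): df = 37, v = 1 + 1/36 = 1.028. At d=0.8 the noncentrality is 0.8/√0.1028 = 2.495 and power is 68.1%. At d=1.107 power is 92.0%.

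Baseline value plus lesion size (k=2): df = 36, v = (1 − R2) × (1 + 2/35) = (1 − R2) × 1.057.

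| R2 of lesion size | v | SE relative to baseline-only, √(v/1.028) | Power, d=0.8 | Power, d=1.107 |
|---|---|---|---|---|
| baseline-only | 1.028 | 1.00 | 68.1% | 92.0% |
| 0 | 1.057 | 1.01 | 66.8% | 91.2% |
| 0.10 | 0.951 | 0.96 | 71.4% | 93.7% |
| 0.20 | 0.846 | 0.91 | 76.3% | 95.9% |
| 0.30 | 0.740 | 0.85 | 81.6% | 97.7% |

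Power with lesion size equals baseline-only power at R2 of about 0.03.

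**4. Adding site as well (k=3).** v = (1 − R2) × (1 + 3/34) = (1 − R2) × 1.088, with R2 now for size and site together. At d=0.8, power is 65.5%, 70.0%, 75.1% and 80.5% for R2 of 0, 0.10, 0.20 and 0.30. At d=1.107 it is 90.4%, 93.0%, 95.4% and 97.4%. Break-even R2 is about 0.06. A simulation of this two-covariate case (5,000 trials per setting, 30% of lesions at the rarer site) agreed: at R2=0.20, about 75% at d=0.8 and 95% at d=1.107.

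**5. One patient fewer per arm.** With 19 analysed per arm, d=1.107 and R2=0, adding lesion size takes power from 90.5% to 89.6%.

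**The case against.** The strongest objection is that nothing here is wrong. Randomisation makes the baseline-adjusted comparison unbiased, and chance imbalance in lesion size is already reflected in its standard error. That stands.

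A second objection is that the gain is speculative, because the documents give no prognostic strength for lesion size and d=0.8 is not a protocol figure. At the design effect, R2=0.10 adds only 1.7 points (92.0% to 93.7%). That also stands, and it is why every gain here is conditional. Preferring lesion size to age, body mass index or chronicity, which are also recorded, is a judgement too.

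Three stronger readings are tempting, and the documents do not support them:

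- A reader might infer that site is recorded for every patient. Eligibility requires it to be known and the operative record may hold it, but it is not a listed data item.
- A reader might infer that precision is certainly being lost. That needs an R2 above the break-even value, and none is given.
- A reader might infer that extra covariates cost only degrees of freedom. In 40 patients chance imbalance also inflates the variance. With R2=0 and d=0.8, size and site together cost 2.6 points (68.1% to 65.5%). If one site is rare, its term rests on a few patients and may bring no gain.

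**Conclusion.** The point holds as a low-cost improvement. A baseline variable that the protocol already collects is left out of the models of a small, unstratified trial. At d=0.8, adding it costs 1.3 points of power if it is not prognostic and gains 3.3 to 13.5 points if R2 lies between 0.10 and 0.30. At d=1.107 with 20 per arm, power stays above the required 90% even in the worst case. With 19 per arm and a non-prognostic covariate it falls just short, at 89.6%.

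These figures rest on the assumed R2 values and on effects scaled to the residual SD. They describe a single two-group comparison at one time point, so they apply directly to the MRI outcome and only by analogy to the repeated PRO measurements. The case for lesion size does not carry over unconditionally to lesion site.

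**What to change.** Before unblinding, amend section 15.0 and the matching synopsis text as follows:

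1. Name lesion size, as a continuous variable, as a covariate alongside the baseline value in the MRI and PRO models. State which measurement of size is used, and add it to the Appendix B schedule.
2. Keep the model with the baseline value alone as a sensitivity analysis.
3. Add lesion site (acetabulum or femoral head) as a covariate only if it is recorded as a baseline field and neither site is rare. Fix the minimum count per site before unblinding.

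The randomisation and sample size need no change. The cost is SAP wording, a schedule entry and, if site is wanted, one data field. The downside is the small loss of power shown above if lesion size turns out not to be prognostic.

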## **16.0 Principal Investigator's Ethical and Regulatory Obligations**

The Principal Investigator is responsible for ensuring that the trial is conducted according to the signed investigator statement, the study protocol and applicable regulations; for protecting the rights, safety, and welfare of subjects under the investigator's care; and for the control of the Study Medication. The Principal Investigator shall confirm informed consent for each subject to whom losartan or placebo, is administered. A discussion of the Principal Investigator's minimal responsibilities follows.

### **16.1 Study Conduct: Ethics and Good Clinical Practice**

Principal Investigator will administer Study Medication only to subjects under his personal supervision or under the supervision of an appropriate Study Team designee responsible to the Principal Investigator.

This study must be carried out in compliance with the protocol and in accordance with the Good Clinical Practice, ICH Guidelines and the Declaration of Helsinki, concerning medical research in humans (Recommendations Guiding Physicians in Biomedical Research Involving Human Subjects, Helsinki 1964, amended Tokyo 1975, Venice 1983, Hong Kong 1989, Somerset West 1996).

The Principal Investigator agrees, when signing the protocol, to adhere to the instructions and procedures described in it and thereby to adhere to the applicable regulatory requirements and to the principles of Good Clinical Practice to which it conforms.

### **16.2 Institutional Review Board**

The Principal Investigator shall assure that an IRB that complies with the requirements set forth in ICH and FDA guidelines will be responsible for the initial and continuing review and approval of the proposed clinical study. The Principal Investigator shall also ensure that he or she will promptly report to the IRB all changes in the research activity and all unanticipated problems involving risk to human subjects or others. Except when the changes constitute minor administrative ones or where necessary to eliminate apparent immediate hazards to human subjects, the Principal Investigator will not make any changes in the research without IRB approval.

Before implementing this study, the protocol, the proposed informed consent form and other subject information, must be reviewed and approved by the Institutional Review Board (IRB).

Other Principal Investigator responsibilities relative to the IRB include the following:

- Submit all protocol amendments to the IRB for review;

---

- Report to the IRB any information about serious AEs reported in other studies associated with treatment;
- Provide the IRB with any other information it requests before or during the conduct of the study;
- Report to the IRB all adverse events as required by the approving IRB(s);
- Maintain a file of IRB/study-related information;
- Update the IRB on a minimum of a yearly basis;
- Maintain IRB approval during the duration of the study.

### **16.3 Informed Consent**

Principal Investigators must explain to each subject the nature of the study, its purpose, the procedures involved, the expected duration, the potential risks and benefits involved and any discomfort it may entail. Each subject must be informed that participation in the study is voluntary and that he or she may withdraw from the study at any time and that withdrawal of consent will not affect his or her subsequent medical treatment or relationship with the treating physician.

This informed consent should be given by means of a standard written statement, written in non-technical language. The subject should read and consider the statement before signing and dating it and should be given a copy of the signed document.

No subject can enter the study before his/her informed consent has been obtained.

The Informed Consent Form must be submitted by the Principal Investigator for IRB approval.

### **16.4 Record Keeping and Study Documents**

Study documents used to record demographic, procedural, and follow-up data, as well as any adverse clinical events that may occur during the study must be retained by the Principal Investigator.

The Principal Investigator must verify personal oversight of the clinical trial and confirm that all data recorded is accurate and current.

All data entries must be made only by the Principal Investigator and/or other site trained personnel. Training will be documented and logged in the site study binder.

#### **16.4.1 Study Medication Accountability**

It is the responsibility of the Principal Investigator to ensure that all Study Medication is inventoried and accounted for throughout the study and recorded in appropriate documents kept in the site study documents.

#### **16.4.2 Records Retention**

All correspondence related to this clinical study should be kept in appropriate study files at the clinical site. Records of subjects, study documents, product inventory, and IRB and Study Team correspondence pertaining to the study must also be kept on file.

The Principal Investigator must retain protocols, amendments, IRB/EC approvals, signed and dated consent forms, source documents, medical records, case report forms, device accountability records, all correspondence and all other documents pertaining to the conduct of the study.

---

**17.0      Disclosure and Confidentiality**

By signing the protocol, the Principal Investigator agree to keep all study documents in strict confidentiality and to request similar confidentiality from his/her staff and the Institutional Review Board. study documents (Protocols, and other material) will be stored appropriately to ensure their confidentiality.

---

**18.0                    Financial Disclosures**

The Principal Clinical Investigator and other key Study Team members shall provide the IRB with sufficient, accurate financial information. Disclosures shall be promptly updated if any relevant changes occur during the course of the Study and for 1 year following the completion of the study.

**19.0                   Interim and Final Study Reports**

Principal Investigators shall furnish all progress reports required by the IRB.

---

**20.0                    Quality Assurance**

**20.1    Subject Completion**

Any subject who does not return for a scheduled follow-up evaluation will be contacted by telephone by the Principal Investigator, or his or her designee, to determine the cause for the missed appointment. Two telephone calls will be made and documented in the study binder, in addition to sending a certified letter requesting the subject to contact the office and return for his/her evaluation. If a returned letter receipt or an undeliverable response is received, this notice will be retained in the subject's study binder that will note the subject is lost to follow-up. If the study subject wishes to withdraw from the study, the reason(s) for discontinuation will be recorded in the subject's chart and on the appropriate study document.

**20.2    Protocol Amendments and Deviations**

No changes in the study procedures shall be effected without documentation by signed protocol amendments. Documentation must include the date and justification for the change and approved by the reviewing IRB prior to implementation of the amendment.

All deviations from the protocol will be recorded from the beginning through the completion of Study Medication administration. The Principal Investigator will be required to assess if any deviation has resulted in additional subject risk, and/or data integrity.

---

**21.0            Declaration of Helsinki**

The study will be conducted according to the guidelines established in the Declaration of Helsinki (World Medical Association 1964). Good Clinical Practices (GCPs) and local ethical and legal requirements. Subjects will be free to withdraw from the study at any stage without prejudice to their subsequent treatment.

**Printed Name of Person Obtaining Consent**

## 23.2 Appendix B – Study Schemata

|  | Standard of Care Used for Screening | Visit 1
POD 1    | Telephone Contact        | Telephone Contact
Day 35 | Visit 2
3 months | Telephone Contact       | Telephone Contact        | Visit 3
18 Months |
|--|-------------------------------------|---------------------|--------------------------|-----------------------------|---------------------|-------------------------|--------------------------|----------------------|
| Window   |                                     | (or upon discharge) | 7-10 days post discharge | +/- 3 days                  | +/- 4 weeks         | 6 months
+/- 4 weeks | 12 months
+/- 8 Weeks |                      |
| I/E Criteria   | X                                   |                     |                          |                             |                     |                         |                          |                      |
| Vitals, H&P  | X                                   |                     |                          |                             | X                   |                         |                          |                      |
| BMI  | X                                   |                     |                          |                             |                     |                         |                          |                      |
| Demographic Info   | X                                   |                     |                          |                             |                     |                         |                          |                      |
| Medical History  | X                                   |                     |                          |                             | X                   |                         |                          |                      |
| Trauma Chronology  | X                                   |                     |                          |                             |                     |                         |                          |                      |
| Circumduction eval   | X                                   |                     |                          |                             | X                   |                         |                          |                      |
| ROM  | X                                   |                     |                          |                             | X                   |                         |                          |                      |
| T2 MRI   | X                                   |                     |                          |                             |                     |                         |                          | X                    |
| Strength Testing   | X                                   |                     |                          |                             | X                   |                         |                          |                      |
| SF-12  | X                                   |                     |                          |                             | X                   | X                       | X                        | X                    |
| Patient Satisfaction   | X                                   |                     |                          |                             | X                   | X                       | X                        | X                    |
| HHS  | X                                   |                     |                          |                             | X                   | X                       | X                        | X                    |
| VHS  | X                                   |                     |                          |                             | X                   | X                       | X                        | X                    |
| HOS  | X                                   |                     |                          |                             | X                   | X                       | X                        | X                    |
| WOMAC  | X                                   |                     |                          |                             | X                   | X                       | X                        | X                    |
| Tegner Activity Scale  | X                                   |                     |                          |                             | X                   | X                       | X                        | X                    |
| VAS  | X                                   |                     |                          |                             | X                   | X                       | X                        | X                    |
| Informed Consent   |                                     | X                   |                          |                             |                     |                         |                          |                      |
| Randomization  |                                     | X                   |                          |                             |                     |                         |                          |                      |
| Medication Pick -up  |                                     | X                   |                          |                             |                     |                         |                          |                      |
| Blood Pressure Cuff, Medication and BP Logs. PT instructions |                                     | X                   |                          |                             |                     |                         |                          |                      |
| Compliance Check   |                                     |                     | X                        | X                           |                     |                         |                          |                      |
| Protocol Deviations  |                                     |                     | X                        | X                           | X                   | X                       | X                        | X                    |
| Adverse Events   |                                     |                     | X                        | X                           | X*                  | X*                      | X*                       | X*                   |
| Basic Metabolic Panel  |                                     |                     | X                        |                             |                     |                         |                          |                      |

\*As related to the target hip only
